**Table 7 - Analysis windows definition for PK and ADA**

Time point	Targeted study day	Analysis window (in study days)
Week 4	29	27 to 31
Week 12	85	83 to 87
Week 24	169	167 to 171
Week 36	253	251 to 255
Week 52	365	363 to 367
Optional: Week 52+ 5 to 10 days	370	370 to 375
Week 64	449	447 to 451

PK concentrations will be analyzed following time windows as defined below in [Table 8](#). If the date of the previous injection is unknown, the SAR156597 concentration will not be considered for the analysis.

**Table 8 - Time windows for PK variables definition**

PK variables	Time
C max	W52 + 5 to 10 days
C trough	-2h (day 1, Weeks 12,24,36,52)
C follow-up	Week 64

### 2.5.5 Unscheduled visits

For all analyses, unscheduled visit measurements may be used to provide a measurement for a time point, a baseline, if appropriate according to their definitions.

### 2.5.6 Pooling of centers for statistical analyses

Not applicable.

### 2.5.7 Statistical technical issues

Not applicable.

### **3 INTERIM ANALYSIS**

As there was no major enrollment issue, no futility analysis was performed.

Early analysis:

The primary analysis of efficacy and safety will be performed on the data collected during the 52-week treatment period. The results of this analysis will not be used to change the conduct of the follow-up in any aspect. The 52-week data will not be reanalyzed at the end of the study. Individuals who have access to patients' source documents will remain blinded with regards to the treatment arm of individual patients throughout the study. Treatment arm will not be disclosed on Data review and Surveillance report.

## 4 DATABASE LOCK

There are two database locks planned for this study as follows:

- First database lock (for early analysis of the main efficacy and safety analyses evaluation at Week 52): 4 weeks after last patient last efficacy visit (Visit 9 Week 52).
- Final database lock (for final analysis of efficacy endpoints and final safety analysis at Week 64): 4 weeks after last patient last visit (Visit 10 Week 64).

## **5 SOFTWARE DOCUMENTATION**

All summaries and statistical analyses will be generated using SAS version 9.4.

## 7 LIST OF APPENDICES

Appendix A: Potentially clinically significant abnormalities (PCSA) criteria

Appendix B: Summary of statistical analyses

Appendix C: Systemic corticosteroids routes

Appendix D: EQ-5D-5L scoring

Appendix E: MedDRA codelists for AESIs

Appendix F: WHODD codelists for prior and concomitant medications

## Appendix A Potentially clinically significant abnormalities criteria

### CRITERIA for POTENTIALLY CLINICALLY SIGNIFICANT ABNORMALITIES – March 2014 for phase 2/3 studies (oncology excepted)

Parameter	PCSA	Comments
Clinical Chemistry		
ALT	By distribution analysis : >3 ULN >5 ULN >10 ULN >20 ULN	Enzymes activities must be expressed in ULN, not in IU/L. Concept paper on DILI – FDA draft Guidance Oct 2007. Internal DILI WG Oct 2008. Categories are cumulative. First row is mandatory. Rows following one mentioning zero can be deleted.
AST	By distribution analysis : >3 ULN >5 ULN >10 ULN >20 ULN	Enzymes activities must be expressed in ULN, not in IU/L. Concept paper on DILI – FDA draft Guidance Oct 2007. Internal DILI WG Oct 2008. Categories are cumulative. First row is mandatory. Rows following one mentioning zero can be deleted.
Alkaline Phosphatase	>1.5 ULN	Enzymes activities must be expressed in ULN, not in IU/L. Concept paper on DILI – FDA draft Guidance Oct 2007. Internal DILI WG Oct 2008.
Total Bilirubin	>1.5 ULN >2 ULN	Must be expressed in ULN, not in $\mu\text{mol/L}$ or $\text{mg/L}$ . Categories are cumulative. Concept paper on DILI – FDA draft Guidance Oct 2007. Internal DILI WG Oct 2008.
Conjugated Bilirubin	>35% Total Bilirubin and TBILI>1.5 ULN	Conjugated bilirubin dosed on a case-by-case basis.
ALT and Total Bilirubin	ALT>3 ULN and TBILI>2 ULN	Concept paper on DILI – FDA draft Guidance Oct 2007. Internal DILI WG Oct 2008. To be counted within a same treatment phase, whatever the interval between measurement.

**CRITERIA for POTENTIALLY CLINICALLY SIGNIFICANT ABNORMALITIES – March 2014  
for phase 2/3 studies (oncology excepted)**

Parameter	PCSA	Comments
CPK	>3 ULN	FDA Feb 2005.
	>10 ULN	Am J Cardiol April 2006. Categories are cumulative. First row is mandatory. Rows following one mentioning zero can be deleted.
CLcr (mL/min)	<15 (end stage renal disease)	FDA draft Guidance 2010
(Estimated creatinine clearance based on the Cockcroft-Gault equation)	≥15 - <30 (severe decrease in GFR)	Pharmacokinetics in patients with impaired renal function-study design, data analysis, and impact on dosing and labeling
	≥30 - <60 (moderate decrease in GFR)	
	≥60 - <90 (mild decrease in GFR)	
	≥90 (normal GFR)	
eGFR (mL/min/1.73m  )	<15 (end stage renal disease)	FDA draft Guidance 2010
(Estimate of GFR based on an MDRD equation)	≥15 - <30 (severe decrease in GFR)	Pharmacokinetics in patients with impaired renal function-study design, data analysis, and impact on dosing and labeling
	≥30 - <60 (moderate decrease in GFR)	
	≥60 - <90 (mild decrease in GFR)	
	≥90 (normal GFR)	
Creatinine	≥150 µmol/L (Adults)	Benichou C., 1994.
	≥30% change from baseline	
	≥100% change from baseline	
Uric Acid		Harrison- Principles of internal Medicine 17 th Ed., 2008.
Hyperuricemia	>408 µmol/L	
Hypouricemia	<120 µmol/L	
Blood Urea Nitrogen	≥17 mmol/L	
Chloride	<80 mmol/L	
	>115 mmol/L	
Sodium	≤129 mmol/L	
	≥160 mmol/L	
Potassium	<3 mmol/L	FDA Feb 2005.
	≥5.5 mmol/L	
Total Cholesterol	≥7.74 mmol/L	Threshold for therapeutic intervention.
Triglycerides	≥4.6 mmol/L	Threshold for therapeutic intervention.
Lipasemia	≥3 ULN	

**CRITERIA for POTENTIALLY CLINICALLY SIGNIFICANT ABNORMALITIES – March 2014  
for phase 2/3 studies (oncology excepted)**

Parameter	PCSA	Comments
Amylasemia	≥3 ULN	
Glucose		
Hypoglycaemia	≤3.9 mmol/L and <LLN	ADA May 2005.
Hyperglycaemia	≥11.1 mmol/L (unfasted); ≥7 mmol/L (fasted)	ADA Jan 2008.
HbA1c	>8%	
Albumin	≤25 g/L	
CRP	>2 ULN or >10 mg/L (if ULN not provided)	FDA Sept 2005.
Hematology		
WBC	<3.0 Giga/L (Non-Black); <2.0 Giga/L (Black) ≥16.0 Giga/L	Increase in WBC: not relevant. To be interpreted only if no differential count available.
Lymphocytes	>4.0 Giga/L	
Neutrophils	<1.5 Giga/L (Non-Black); <1.0 Giga/L (Black)	International Consensus meeting on drug-induced blood cytopenias, 1991. FDA criteria.
Monocytes	>0.7 Giga/L	
Basophils	>0.1 Giga/L	
Eosinophils	>0.5 Giga/L or >ULN (if ULN ≥0.5 Giga/L)	Harrison- Principles of internal Medicine 17 th Ed., 2008.
Hemoglobin	≤115 g/L (Male); ≤95 g/L (Female) ≥185 g/L (Male); ≥165 g/L (Female)  Decrease from Baseline ≥20 g/L	Criteria based upon decrease from baseline are more relevant than based on absolute value. Other categories for decrease from baseline can be used (≥30 g/L, ≥40 g/L, ≥50 g/L).
Hematocrit	≤0.37 v/v (Male) ; ≤0.32 v/v (Female) ≥0.55 v/v (Male) ; ≥0.5 v/v (Female)	
RBC	≥6 Tera/L	Unless specifically required for particular drug development, the analysis is redundant with that of Hb. Otherwise, consider FDA criteria.
Platelets	<100 Giga/L ≥700 Giga/L	International Consensus meeting on drug-induced blood cytopenias, 1991.
Urinalysis		
pH	≤4.6 ≥8	

**CRITERIA for POTENTIALLY CLINICALLY SIGNIFICANT ABNORMALITIES – March 2014  
for phase 2/3 studies (oncology excepted)**

Parameter	PCSA	Comments
Vital signs		
HR	≤50 bpm and decrease from baseline ≥20 bpm ≥120 bpm and increase from baseline ≥20 bpm	To be applied for all positions (including missing) except STANDING.
SBP	≤95 mmHg and decrease from baseline ≥20mmHg ≥160 mmHg and increase from baseline ≥20 mmHg	To be applied for all positions (including missing) except STANDING.
DBP	≤45 mmHg and decrease from baseline ≥10 mmHg ≥110 mmHg and increase from baseline ≥10 mmHg	To be applied for all positions (including missing) except STANDING.
Orthostatic Hypotension		
Orthostatic SDB	≤-20 mmHg	
Orthostatic DBP	≤-10 mmHg	
Weight	≥5% increase from baseline ≥5% decrease from baseline	FDA Feb 2007.
ECG		
		Ref.: ICH E14 guidance (2005) and E14 Q&A (2012), and Cardiac Safety Research Consortium White Paper on PR and QRS (Nada et al. Am Heart J. 2013; 165(4) : 489-500)
HR	<50 bpm <50 bpm and decrease from baseline ≥20 bpm <40 bpm <40 bpm and decrease from baseline ≥20 bpm <30 bpm <30 bpm and decrease from baseline ≥20 bpm >90 bpm >90 bpm and increase from baseline ≥20bpm >100 bpm >100 bpm and increase from baseline ≥20bpm >120 bpm >120 bpm and increase from baseline ≥20 bpm	Categories are cumulative       Categories are cumulative

**CRITERIA for POTENTIALLY CLINICALLY SIGNIFICANT ABNORMALITIES – March 2014  
for phase 2/3 studies (oncology excepted)**

Parameter	PCSA	Comments
PR	>200 ms	Categories are cumulative
	>200 ms and increase from baseline $\geq 25\%$	
	>220 ms	
	>220 ms and increase from baseline $\geq 25\%$	
	>240 ms	
	>240 ms and increase from baseline $\geq 25\%$	
QRS	>110 ms	Categories are cumulative
	>110 msec and increase from baseline $\geq 25\%$	
	>120 ms	
	>120 ms and increase from baseline $\geq 25\%$	
QT	>500 ms	
QTc	Absolute values (ms)	To be applied to any kind of QT correction formula.
		Absolute values categories are cumulative
	>450 ms	
	>480 ms	
	>500 ms	QTc >480 ms and $\Delta QTc > 60$ ms are the 2 PCSA categories to be identified in individual subjects/patients listings.
	Increase from baseline	
	Increase from baseline ]30-60] ms	
Increase from baseline >60 ms		

## Appendix B Summary of statistical analyses

### *EFFICACY ANALYSIS*

Endpoint	Analysis population	Primary analysis	Supportive analysis	Subgroup analysis	Other analyses
Primary endpoint					
%predicted FVC: Change from baseline at week 52	mITT	Rank ANCOVA with adjustment covariates: stratification factor (with/without Background Therapy), %predicted FVC baseline; and a treatment fixed effect. Imputation of W52 values using linear regression (according to treatment arm and treated status 52 weeks), time-to-death for ranking deaths and time-to-lung transplants for ranking lung transplants.	MMRM with treatment arm, stratification factor, % predicted FVC baseline, time point, treatment-by-time point interaction, stratification factor-by-treatment-by-time point interaction. Multiple imputation of W52 values using CIR (other) and translated distribution of their last available assessments (death or lung transplant).	Subgroups: Gender, age ≤65 or <65, Smoking status, with/without Background Therapy, Baseline %predicted FVC% categories, ANA at baseline (Positive/Negative) using both rank ANCOVA model and MMRM.	MMRM on-treatment data with treatment arm, stratification factor, % predicted FVC baseline, time point, treatment-by-time point interaction, stratification factor-by-treatment-by-time point interaction. No imputation.  Cumulative distribution of decline from baseline at 24 weeks and at 52 weeks in % predicted FVC
Secondary endpoints					
Time-to-disease progression at 52 weeks: time-to-first event between a decrease in change from baseline in %predicted FVC≥10%, a decrease in change from baseline in %predicted DLCO≥15%, death and lung transplant.	mITT	Log-rank stratified on stratification factor (with/without Background Therapy); Kaplan-Meier representation and Hazard Ratio using a Cox model with treatment, stratification factor,. No imputation.	No	Subgroups: Gender, age≤65 or <65, Smoking status, with/without Background Therapy, Baseline %predicted FVC% categories, ANA at baseline (Positive/Negative).	Time-to-disease progression at 24 weeks: Hazard Ratio using a Cox model with treatment, stratification factor , stratification factor-by-treatment. No imputation.

Endpoint	Analysis population	Primary analysis	Supportive analysis	Subgroup analysis	Other analyses
Cumulative incidence of all-cause mortality	mITT	Kaplan-Meier representation and Hazard Ratio using a Cox model with treatment, stratification factor ,. No imputation.	No	No	IPF-related deaths: Kaplan-Meier representation and Hazard Ratio using a Cox model with treatment, stratification factor , stratification factor-by-treatment. No imputation.
Exploratory endpoints					
Change from baseline to week 52 in %predicted DLCO	mITT	MMRM with treatment arm, stratification factor, time point, treatment-by-time point interaction, stratification factor-by-treatment-by-time point interaction, % predicted DLCO baseline.No imputation.	No	No	No
Annual rate of acute IPF exacerbations	mITT	Annual rate from negative binomial model adjusted on stratification factor (with/without Background Therapy) and stratification factor-by-treatment interaction. No imputation.	No	No	No
Annual rates of respiratory and non-elective hospitalizations	mITT	Annual rates from negative binomial model adjusted on stratification factor (with/without Background Therapy) and stratification factor-by-treatment interaction. No imputation.	No	No	No
Change from baseline to week 52 in 6-MWT distance	mITT	MMRM with the fixed categorical effects of treatment arm, stratification factor, time point, treatment-by-time point interaction, stratification factor-by-treatment-by-time point interaction, supplemental oxygen use at baseline, 6-MWT distance at baseline. No imputation.	No	No	No

Endpoint	Analysis population	Primary analysis	Supportive analysis	Subgroup analysis	Other analyses
Change from baseline to week 52 in HRCT lung interstitial score (Total Fibrosing ILD score)	mITT	Ancova with baseline value, emphysema score at baseline, stratification factor, treatment, stratification factor-by-treatment interaction. No imputation.	No	No	No
Change from baseline to week 52 in SGRQ	mITT	MMRM with treatment arm, stratification factor, time point, treatment-by-time point interaction, stratification factor-by-treatment-by-time point interaction, SGRQ total score at baseline. No imputation.	No	No	No
Change from baseline to week 52 in EQ-5D-5L	mITT	MMRM with treatment arm, stratification factor, time point, treatment-by-time point interaction, stratification factor-by-treatment-by-time point interaction, as EQ-5D-5L total score at baseline . No imputation.	No	No	No

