### **1.3 DETERMINATION OF SAMPLE SIZE**

Approximately 300 patients will be randomized in this study, 100 per treatment arm. Based on the enrollment in prior studies of this population approximately half of the patients are expected to be older than 65.

The sample size calculations are based on the primary efficacy variable of % predicted FVC change from baseline to week 52, with the following assumptions:

- A common standard deviation of 12% is assumed based on the data from previous trials (26)
- A 5% mean difference between each dose and placebo in change from baseline in % predicted FVC
- A 2-sided 5% significance level with 80% power

Ninety two (92) patients per treatment arm will yield 80% power to detect a 5 percentage point difference between the treatment groups and placebo. Additional patients will be randomized in each regimen to allow for dropouts; therefore, approximately 100 patients will be randomized into each treatment arm, for a total sample size of approximately 300 patients for the study.

[figure not shown]
As a rank-based method will be used for analysis the actual power may differ from these calculations, however, calculations based on the ASCEND study (28), which used the same analysis method and endpoint confirm that the planned analysis should have at least 80% power. No adjustment is made for multiplicity since a hierarchical testing procedure is proposed.

Calculations were made using nQuery Advisor 7.0.

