- Description of each component as individual (all events will be considered meaning that a patient could be represented several times per component): their number of events, event rates, their estimated hazard ratios and their 90 and 95% CIs

In addition, the maximal absolute decrease in % predicted FVC and the maximal absolute decrease in %predicted DLCO will be described by categories ( $\geq 0$  and  $< 5\%$ ,  $\geq 5\%$  and  $< 10\%$ ,  $\geq 10\%$  and  $< 15\%$ ,  $\geq 15\%$  and  $< 20\%$ ,  $\geq 20\%$ ) at 52 weeks. Decomposition of events and maximal events will be explored at 24 weeks as well.

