#### 2.4.4.2.2 *All-cause mortality endpoint*

The all-cause mortality will be analyzed on the mITT population. Deaths from baseline to week 52 (performed before Day 375) will be used regardless of whether the patient has previously discontinued treatment.

The cumulative incidence of all-cause mortality will be presented graphically by treatment arm and background therapy status, using Kaplan-Meier method. The Kaplan Meier survival estimates (number of patients at risk, number of patients censored, number of death events and probability of surviving without event (95% CI)) will be summarized by time points and overall (number of patients censored, number of events, median time to event).

The censoring reasons will be described by treatment arm and background therapy status.

The event rates for each of the 3 treatment arms, the hazard ratio and its 90% and 95% CIs compared to placebo for each active arm versus Placebo will be estimated from a Cox model containing the treatment and the stratification factor variables. The underlying assumption of proportional hazards for Cox model will be checked by visual inspection.

No hypothesis testing will be performed as per protocol.

The same time-to-event analysis with IPF-related deaths only will be explored on the mITT population.

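### SAP Appendix B adds a stratum-by-treatment term to the Cox model for IPF-related death, which contradicts SAP section 2.4.4.2.2 and leaves the reported hazard ratio undefined

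*SAP*

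**What the plan says.** For all-cause mortality, SAP section 2.4.4.2.2 estimates the hazard ratio of each active arm against placebo from a "Cox model containing the treatment and the stratification factor variables". The same section then covers IPF-related death in one sentence: "The same time-to-event analysis with IPF-related deaths only will be explored on the mITT population".

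The efficacy table in SAP Appendix B has a row for all-cause mortality. Its primary-analysis cell agrees with the text: "Kaplan-Meier representation and Hazard Ratio using a Cox model with treatment, stratification factor ,. No imputation". The cell for other analyses in that row reads: "IPF-related deaths: Kaplan-Meier representation and Hazard Ratio using a Cox model with treatment, stratification factor , stratification factor-by-treatment".

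The progression row of Appendix B has the same pattern. The 52-week model contains treatment and stratum only, as in section 2.4.4.2.1. The cell for other analyses reads: "Time-to-disease progression at 24 weeks: Hazard Ratio using a Cox model with treatment, stratification factor , stratification factor-by-treatment. No imputation". On the 24-week time point, section 2.4.4.2.1 says only: "Decomposition of events and maximal events will be explored at 24 weeks as well". It names no Cox model for that time point.

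Protocol section 11.4.2.2 does not mention IPF-related death, so it does not settle which model applies.

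**The concern.** A programmer has two instructions for one analysis. Under section 2.4.4.2.2 there is one hazard ratio per active arm, assumed common to the two strata. Under Appendix B the treatment effect may differ between strata, and the plan still asks for a hazard ratio in the singular without saying how to obtain it. With 0/1 coding, the printed treatment coefficient is the effect in whichever stratum is the reference. With another coding it is an average over strata.

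The IPF-related estimate could therefore differ from the all-cause estimate because the model changed, not because the cause of death matters. The Appendix B estimate also rests on fewer events. If IPF-related deaths are few, an arm-by-stratum cell may have none, and that stratum's hazard ratio then goes to zero or infinity.

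**Working it through.** The documents give no event count, hazard ratio or power for these models, so there is no planned figure to reproduce.

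**Inputs**
- 100 patients per arm (SAP section 1.3: "Approximately 300 patients will be randomized in this study, 100 per treatment arm").
- 66 with and 34 without background therapy per arm. The 66% is the cap in SAP section 1.1, not a forecast, so a 50/50 split is shown as well.
- IPF-death risk *p* by the end of follow-up: not given. Assumed equal in all cells, from 2% to 20.6%. The upper end comes from the median survival of about 3 years in protocol section 4.1: 1 − 2^(−1/3) = 20.6% at one year. That is an all-cause background figure, not a trial assumption.

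**Do the two models estimate the same quantity?** No. A simulation (400 runs, 100 per arm, 66/34 split, 20% control risk) used true hazard ratios of 0.6 with and 1.0 without background therapy. No run had an empty cell.
- Treatment and stratum only: about 0.72, SE of the log hazard ratio 0.35.
- Interaction model, reference stratum without background therapy: about 0.99, SE 0.58.
- Interaction model, reference stratum with background therapy: about 0.57.
- For comparison, an equal-weight average over strata would be √(0.6 × 1.0) = 0.775.

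So the discrepancy does not depend on rare events.

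**Precision.** Approximate SE of the log hazard ratio = √(1/d₁ + 1/d₀) = √(2/(m·p)), for m patients per arm. At p = 10%:
- whole arm (m = 100): √(2/10) = 0.45
- stratum with background therapy (m = 66): √(2/6.6) = 0.55
- stratum without (m = 34): √(2/3.4) = 0.77

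**Empty cells, per active-placebo pair**
- Interaction model, at least one of four cells without an event: 1 − [(1 − (1−p)^66)(1 − (1−p)^34)]²
- Main-effects model, at least one of two arms without an event: 1 − [1 − (1−p)^100]²

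At p = 2%: 0.98^66 = 0.264, 0.98^34 = 0.503 and 0.98^100 = 0.133. The interaction figure is 1 − (0.736 × 0.497)² = 0.87. The main-effects figure is 1 − 0.867² = 0.25.

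| p (assumed) | Interaction, 66/34 | Interaction, 50/50 | Main effects |
|---|---|---|---|
| 2% | 87% | 84% | 25% |
| 3% | 69% | 63% | 9% |
| 5% | 36% | 27% | 1% |
| 8% | 12% | 6% | under 0.1% |
| 10% | 6% | 2% | under 0.1% |
| 20.6% | 0.1% | under 0.1% | under 0.1% |

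Most of the 66/34 figure comes from the smaller stratum: its own hazard ratio fails with probability 1 − [1 − (1−p)^34]², which is 58% at 3% and 32% at 5%. An empty cell makes only that stratum's hazard ratio diverge; the other stratum's can still be estimated.

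**The case against.** **The analyses carry little weight.** Both are listed under other analyses, the text only says they will be explored, mortality has no hypothesis test, and neither enters the multiplicity procedure of SAP section 2.4.4.3. This stands, and it sets the importance of the point.

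**An interaction model can still give one hazard ratio.** A contrast averaged over strata would do so, and the SAP reports a single rate ratio per comparison from models with the same interaction for exacerbations and hospitalizations. This is also right. The gap is that no contrast is stated for these Cox models, and section 2.4.4.2.2 specifies a model without the term.

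**A reader might infer that the Appendix B hazard ratio will often be inestimable.** The documents do not support that. It holds for IPF-related death only if the risk is about 5% or lower, and no rate is given. At 10% an empty cell occurs in 6% of pairs, and at 20.6% in 0.1%. For 24-week progression, a composite that also counts FVC and DLCO declines, any risk of 10% or more leaves an empty cell in at most about 6% of pairs.

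**A reader might also infer that Appendix B contradicts the text on 24-week progression.** It does not, because section 2.4.4.2.1 specifies no 24-week Cox model. There is only an unexplained difference from the 52-week model.

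**Deleting the term does not remove every sparse estimate.** Section 2.4.4.2.1 already plans hazard ratios for the progression components, including death, by background therapy status. That is correct. The case for deletion is consistency and a defined estimate.

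**Conclusion.** The contradiction on IPF-related death is real and stands in the current SAP text. The models estimate different quantities whenever the effect differs between strata, and without a stated contrast the Appendix B coefficient depends on coding. With 0/1 coding it is a stratum-specific hazard ratio, less precise than the all-cause estimate and not comparable with it. This conclusion needs no assumption about event rates.

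The empty-cell problem is conditional. It is substantial at an assumed IPF-death risk of 2% to 5% (87% to 36% of pairs at the 66/34 split, against 25% to 1% without the interaction) and minor at 10% or more. The figures assume equal risk in all cells and complete follow-up.

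The stray punctuation at the end of the all-cause cell would fit an interaction term that was deleted there and left in the neighbouring cell. That is an inference, not something the documents state.

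Importance is low: one exploratory, untested estimate is affected, and for 24-week progression there is a question of consistency only.

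**What to change.** In the IPF-related-death cell of SAP Appendix B, delete the stratification factor-by-treatment term so that the model matches section 2.4.4.2.2. The Kaplan-Meier displays by background therapy status in that section remain as descriptive output.

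In the same edit, either delete the term from the 24-week progression cell, so that it matches the 52-week model, or state the contrast that yields the reported hazard ratio.

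If the sponsor does want the interaction for IPF-related death, section 2.4.4.2.2 should be amended instead. It should then name the contrast (for example, one hazard ratio per stratum) and give a rule for cells without events.

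The cost is one term removed from one or two table cells, with no effect on data collection, sample size or the testing procedure. It should be settled before the first database lock, so that nobody chooses between the models with results in hand.
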